**Developing Process-Specific Verbal Memory
Interventions for Veterans with TBI**

Protocol

NCT02310633

March 4, 2019

Protocol

1. Project Title: Developing Process-Specific Verbal Memory Interventions in Veterans with TBI

2. Investigator(s): [name]., [name]., [name].

3. Abstract: Memory dysfunction can result from impairments along a continuum of information processing, from poor initial acquisition of information during learning to disturbed retrieval of stored memory when it is later needed to perform a task¹. There is a critical need to better understand disease heterogeneity in order to enhance diagnosis and therapeutic management². Several subtypes of memory dysfunction after TBI have been identified^{3,4}. First, some TBI survivors exhibit impaired memory acquisition/encoding (e.g., frontal system damage)⁵. Second, some exhibit impaired memory consolidation/storage impairment (e.g., prominent damage to temporal lobe systems⁶). Third, some show impairment in retrieval of information^{5,7}. This heterogeneity results from the variable nature and severity of underlying brain trauma resulting from unpredictable mechanical forces^{2,8}. This study attempts to determine whether these subtypes of memory respond better to treatments that are focused specifically on the constituent cognitive deficit than to other treatments. There are existing training protocols for training these three components of memory processing, as follows: encoding (memory strategy training⁹), consolidation (errorless learning¹⁰), and retrieval (retrieval practice¹¹, but their efficacy has not been tested in TBI survivors with documented impairments in each component. That is, to our knowledge, there is no solid evidence for memory training in TBI survivors that supports the widely held belief that specifically matching the patient impairment to the treatment leads to better treatment outcomes. This project attempts to fill this gap in our knowledge. In an alternating treatments design, TBI survivors with encoding, consolidation, or retrieval deficits will undergo (a) a treatment matched to their deficit and (b) a treatment that addresses a different deficit. High resolution imaging and neurocognitive biomarkers will be used to predict response to treatment. Results will be used as a basis for a larger clinical trial of memory rehabilitation in brain injured populations.

4. Background:

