Aim 2. Aim 2 is to provide a preliminary test of the response to the three memory interventions. At baseline, TBI survivors will be evaluated for memory function in each of these three memory component processes using established neuropsychometric methods. Their experimental treatment allocation will be to the treatment targeting their most impaired memory component. In addition, each subject will serve as his/her own control, by engaging in a treatment targeted to another memory component ('mismatched' group).

Hypothesis A. The matched vs. mismatched group will show differential improvement in memory component function, with the former group benefitting to a significantly greater degree. (Primary measures: Memory component performance, encoding, consolidation, retrieval; secondary: cognitive function and quality of life).

Aim 3. Aim 3 is to establish links between the behavioral taxonomy of the three memory components and differences in brain structure and function documented with diffusion tensor imaging and functional connectivity analysis. This is a key first step in establishing brain-based metrics of neuroplastic change after memory therapy in our research program.

Objective 3.1. Identify specific and unique imaging signatures that distinguish patients with deficits in encoding, consolidation, and retrieval, respectively. Primary measures: structural measures of morphometry and white matter integrity (FA) and functional connectivity (cross correlation and total interdependence) in identified brain networks damaged in TBI.

Clinical Implications. This research has the potential to devise a method to match specific

subcomponents of memory impairment to specifically targeted memory interventions, thus maximizing recovery of memory and function. The results of this investigation will be used to refine the interventions, to evaluate cognitive and functional endpoints, and to power a larger clinical trial that will yield data enabling clinicians to match TBI patients to effective treatments based on their individual profile of memory dysfunction.

6. Research Plan:

6.1. Study Design. The proposed research will be conducted in three phases: Intervention Development, Patient Characterization and Classification, and Initial Testing of Treatment Efficacy.

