6.2. Phase 1: Intervention Development. During the first 6 months of the project, we will formalize, manualize, and perform preliminary fidelity testing on three memory interventions targeting process-specific memory deficits after TBI in Veterans: (a) memory strategy training (to boost encoding), (b) errorless learning (to improve consolidation, and (c) retrieval practice (to rehabilitate deficits in retrieval).

6.2.1. Materials Common to Memory Interventions. Each of the three treatment conditions will utilize the same training materials, a set of verbal paired-associates (VPA) and a set of face-name pairs (FNP), both presented for training in associative learning. Each session will involve training utilizing two 12-item VPA lists and two sets of 12 FNP's, for an overall total of 144 unique VPAs and 144 FNPs. The VPA's are weak paired associates^{26,27} (have a forward association strength of <.01²⁸), and that do not contain words from clinical memory tests given in Phase 2. FNP's are constructed by pairing face-front black and white photographs from Stringer's Ecologically-Oriented Neurorehabilitation of Memory (EON-MEM) protocol²⁹. Training stimuli will be presented on a desktop computer using E-prime software.

6.2.2. Memory Strategy Training (MST). MST, in which persons with brain injury are taught specific strategies useful for encoding new information at the point of learning, is a widely used rehabilitative technique^{9,30,31} that is an *ACRM practice standard*¹⁵. While specific strategies vary across studies, most teach the participant to form meaningful cognitive associations between memoranda through the use of imagery or semantic encoding, building a form of memory encoding known as relational memory³². Relational encoding, a key process that enhances the strength and durability of episodic memory^{33,34}, can be reduced or impaired after TBI³⁵. Successful relational memory involves two distinct mnemonic mechanisms: the generation of an association between to-be-encoded items (a frontal/executive function)^{36,37} and the binding of that association into a cohesive memory trace (a function of the hippocampal memory system)^{33,38}. MST may be particularly useful in enhancing the first of these two processes.

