6.4. Phase 3: Initial Testing of Treatment Efficacy

6.4.1. Overview. In this phase, appropriately classified patients will be assigned to participate in two memory interventions, one matched to their primary deficit, the other

mismatched, in counterbalanced order. The overall framework is outlined in Table 4; shaded cells are “matched” conditions.

6.4.2. Design. The overall approach is a ***multiple-subject Alternating Treatment Design***, effective for determining the relative efficacy of two treatments in a single individual⁸⁰. One participant will be assigned to each treatment order in Table 4, such that 4 patients per classification group (12 total) will participate. Each participant will receive 1 matched and 1

Table 4. Treatment Schedule

Memory Deficit	Treatment Strategy/Target			Treatment Orders (one matched, one mismatched; counterbalanced)
	Memory Strategy Training (1)	Errorless Learning (2)	Retrieval Practice (3)	
Encoding	+/+	+/-	+/-	12, 13, 21, 31
Consolidation	-/+	+//	+/-	21, 23, 12, 32
Retrieval	-/+	-/+	+//	31, 32, 13, 23

mismatched treatment, in counterbalanced order. Therapists will be blinded to patient classification.

Although this design is subject to multiple-treatment interference⁸¹ (the notion that the effects of each of the interventions might be affected by the presence of another intervention), such

[figure not shown]

Figure 1. Hypothetical data of two patients, one with encoding deficit (blue), the other with retrieval deficit (red).

carryover effects are typically small and counterbalancing the order of treatments should further reduce treatment carryover⁸⁰. The design permits comparison of treatment effects in conditions in which a treatment is given first vs. second. New methods for calculating treatment effect size and possible confounding factors are available⁸²⁻⁸⁵. ***It is hypothesized that greater gains in memory will be seen in matched, as compared to unmatched, treatments.*** This is illustrated by hypothetical data presented in Figure 1, where a patient with encoding deficits (blue) benefits more [greater elevation and slope] from memory strategy training than from retrieval practice, while the opposite pattern is seen

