in the patient with retrieval deficits (red). Each treatment will be conducted twice weekly for 3 weeks (6 sessions). Thus, each participant's involvement in actual treatment will span 6 weeks (2 treatments). Participants will be offered \$20/session for participation as inconvenience cost and to help them defray travel expenses. We will conduct a 1-month follow-up at which time performance on proximal outcomes (performance on VPA and FNP tasks) and secondary outcomes (see below) will be evaluated.

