## 2.6. Statistical Analysis Plan

The procedure for classifying participants into Encoding, Consolidation, and Retrieval groups is outlined in Section 2.3.2. It is recognized that, although patients will be classified according to their primary memory deficit, some may have relevant impairment in more than one domain. For this reason, each participant will be given a composite score for encoding, consolidation, and retrieval, and all three of these composite scores will be used in exploratory analyses of predictors of treatment response. Phase 2 neuropsychological scores (z-score transformed data using appropriate age- and education corrections) and neuroimaging data (NEW, FA, diffusivity measures, morphological volumes, TI from RS-fMRI for specific ROI pairs) will be analyzed using 1-way (Group: Encoding, Consolidation, Retrieval) ANOVAs followed by pairwise follow-ups with the Tukey HSD test. Dependent variables used to evaluate memory performance in Phase 3 are detailed in Section 2.2 above, and include session-wise percent correct data on VPA and FNP memory probes as well as post-treatment and 1-month follow-up probes. Data from Phase 3 will be analyzed by comparing effect sizes of matched and unmatched treatments at the individual subject level using methods described by Parker et al. These measures include (a) percentage of non-overlapping data points, (b) quantitative measures of improvement rate and difference level, and (c) Tau-U, a nonparametric measure of effect size that tests for differences in two treatments after trend adjustment. Additional measures will also be explored, including interrupted time-series/regression approaches and the last-day-of-treatment comparison approach. We will also evaluate the separate influence that severity of memory deficit has on treatment response (independent of patient grouping) by performing hierarchical linear regression in which severity is coded as average z-score on memory indices derived from phase 2, and patient grouping is dummy-coded.

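### SAP 2.6 specifies no across-person matched-minus-unmatched estimate, SD or interval, although the protocol states a group-level hypothesis and intends the results to power a larger trial

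*Protocol*

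**What the plan says.** Protocol section 5, Aim 2, Hypothesis A, is worded as a group claim: "The matched vs. mismatched group will show differential improvement in memory component function, with the former group benefitting to a significantly greater degree". The Clinical Implications paragraph of the same section says the results will serve, among other uses, "to power a larger clinical trial that will yield data enabling clinicians to match TBI patients to effective treatments". The abstract says the same in general terms: "Results will be used as a basis for a larger clinical trial of memory rehabilitation in brain injured populations".

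Protocol section 6.4.2 assigns one participant to each treatment order, "such that 4 patients per classification group (12 total) will participate". Each participant has six sessions of a matched treatment and six of an unmatched one.

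SAP section 2.6 then says: "Data from Phase 3 will be analyzed by comparing effect sizes of matched and unmatched treatments at the individual subject level". The named measures are (a) percentage of non-overlapping data points, (b) measures of improvement rate and level difference, and (c) Tau-U. Time-series or regression methods and a last-day comparison are to be explored, with no level of analysis given. A hierarchical linear regression across participants examines whether severity of memory deficit affects treatment response.

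None of these is said to give the mean matched-minus-unmatched difference across participants, its SD or an interval, and no rule combines the 12 individual results. Section 2.6 names none of the secondary outcomes in protocol Table 5.

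**The concern.** A claim that matched treatment helps significantly more is a statement about the average across people. Twelve separate person-level effect sizes, with no rule for combining them, do not answer it.

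Sizing a later trial needs a difference on the outcome scale and the SD that goes with the later design: the SD of within-person differences for a crossover, or the between-person SD for a parallel-group trial. The supplied SAP text plans neither. Non-overlap and Tau-type indices do not replace them directly. They reach their limit once every session under one treatment exceeds every session under the other, so any further gain leaves them unchanged. They also depend on how much one person's scores vary from session to session, not on how much people differ from each other.

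Table 5 shows the gap most clearly. Those measures are taken before treatment, once at the end of each treatment, and at one month. With one score per treatment there is no session series on which to compute non-overlap or Tau-U.

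If the plan stays as it is, the group-level answer and the inputs to the next trial will rest on choices made after the data are seen.

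**Working it through.** **The plan's own figure.** 4 treatment orders × 3 deficit groups × 1 participant = 12, as stated. This is a counterbalancing count. The documents give no alpha, power, target difference or SD for this study or the larger trial, so there is no power figure to reproduce.

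**Inputs from the documents.** 12 participants; 6 sessions per treatment; two 12-item lists per task per session, so 24 items per task.

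**Assumed, for illustration only.** Two-sided 5%, 80% power and a target difference δ of 10 percentage points. Session SD sw = √(0.5 × 0.5 / 24) = 0.102, or 10.2 points (binomial, 24 items at 50% correct).

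**Sizing on session scatter.** This stands in for reading a single-case effect as a between-person standardised difference.
- Parallel, per arm: n = 2(1.96 + 0.84)²(SD/δ)² = 15.7 × (10.2/10)² = 16.3, so 17.
- Crossover, total: n = (1.96 + 0.84)²(SD/δ)² = 7.85 × (10.2/10)² = 8.2, so 9.

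**Sizing on the SD that applies to 6-session means.** Let sb be the between-person SD of the level and tau the between-person SD of the true matched-minus-unmatched difference.
- Parallel: SD = √(sb² + sw²/6).
- Crossover: SD = √(tau² + 2sw²/6).

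| sb (points) | Needed per arm | Power at 17 per arm |
|---|---|---|
| 5 | 7 | 99% |
| 10 | 19 | 77% |
| 15 | 39 | 47% |
| 20 | 66 | 30% |
| 25 | 101 | 21% |

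| tau (points) | Needed in total | Power at 9 in total |
|---|---|---|
| 0 | 3 | 99.9% |
| 5 | 5 | 97% |
| 10 | 11 | 73% |
| 15 | 21 | 46% |
| 20 | 35 | 30% |

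**Break-even.** The two approaches agree when sb = sw√(1 − 1/6) = 0.91 sw = 9.3 points, or tau = sw√(1 − 2/6) = 0.82 sw = 8.3 points. Above these values the larger trial is too small; below them it is too large. With a session SD of 14.4 (one 12-item list) the break-evens move to 13.1 and 11.8 points.

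**Is the index itself at fault?** Tau without trend adjustment was simulated for 20,000 persons with 6 against 6 sessions. Sizing a crossover on the mean and SD of personal Tau values gave 10 where the raw differences gave 11 (tau = 10), and 36 where they gave 35 (tau = 20). What is missing is the across-person summary; the index is not the cause.

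**What 12 participants can say.** An SD on 11 df has a 95% interval from √(11/χ²(0.975)) = 0.71 to √(11/χ²(0.025)) = 1.70 times the estimate. Squared, that is a 0.50- to 2.88-fold range in N. Within one deficit group of 4 (3 df) the limits are 0.57 and 3.73.

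**The case against.** The strongest reply is that section 2.6 is not confined to overlap indices. Measure (b) may give a raw person-level difference, and the section also lists regression and last-day approaches and an across-person regression. The session-wise percent-correct scores are collected, so a mean and SD could be computed later with nothing lost. The design of the larger trial belongs in its own protocol.

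Much of this stands. It would be wrong to say that the SAP yields nothing but single-case indices, or that non-overlap and Tau-U are divided by a session SD; they depend on session scatter but are not scaled by it. How the later trial chooses its target difference or allows for an imprecise SD is a matter for that protocol. The reply does not supply the missing quantity, however: none of the listed methods is said to produce the matched-minus-unmatched mean and its SD across people, and a quantity chosen after the data are seen is not pre-specified.

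A reader might also infer that the larger trial would be undersized, by the square of the ratio of between-person to session SD. A ratio of 2, for example, would mean 63 per arm (15.7/0.5²) instead of 16 (15.7/1.0²). The documents do not support that. They nowhere say that these indices will be entered in a sample-size formula, and they give no SD, endpoint or design for the larger trial. For 6-session means the direction reverses below the break-even. Undersizing whatever the value of sb follows only in the special case of a parallel trial scored on a single session (at sb = 20, 80 per arm needed against 17).

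**Conclusion.** The concern holds as a gap between stated purpose and planned analysis. The protocol states a group-level hypothesis and intends to power a larger trial, while the supplied SAP text specifies no across-person estimate of the matched-minus-unmatched difference, no SD and no interval.

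Using the single-case indices directly as a between-person effect could mis-size the larger trial either way. Undersizing follows if people differ widely, which is plausible given the heterogeneity the protocol describes in section 4, but the documents do not establish it. The sample sizes above rest on an assumed 10-point difference, 5% two-sided alpha, 80% power and a binomial session SD, and show direction only. The 0.71 to 1.70 interval needs no assumed SD; it rests on 12 complete participants and roughly normal differences.

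Part of the SAP document is not in the supplied text, so the conclusion covers section 2.6 as supplied. The change should be made: it lets the plan address its own hypothesis and stated use.

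**What to change.** Add to SAP section 2.6, for VPA and FNP percent correct and for each Table 5 measure taken at the end of each treatment:

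- The matched-minus-unmatched difference for each participant, with its definition (for Table 5, whether it contrasts end-of-treatment scores or changes over each treatment).
- Across the 12 participants, the mean of that difference, the SD of within-person differences and the between-person SD, each with a 95% interval. A mixed model with person, order and period terms is one way to obtain these.
- A statement that an SD from 12 participants (11 df) has a 95% interval of about 0.71 to 1.70 times the estimate, and wider if model terms use up degrees of freedom.
- A statement that non-overlap, improvement rate and level, and Tau-U are kept as person-level descriptions.

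The cost is a few lines of SAP text and slightly more analysis, with no new visits, measures or participants. The drawback is that the wide intervals will show how little 12 participants can say about the average effect or its spread.

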6.2.2.1. Procedure. Six biweekly sessions of MST will be conducted. Two VPA lists and two FNP lists will be used in each session. During MST, VPAs (e.g., "candle-table") or FNPs will be presented in horizontal arrangement on a computer screen at a rate of 1 per 6 seconds (this may be modified based on participant processing speed). For **VPA learning**, participants will be asked to generate a memorable sentence (first list) or form a distinctive mental image (second list) that links the two VPA items together. The therapist will help the participant generate sentences and images that are distinctive or unusual, and therefore more memorable. Specific examples of distinctive sentence-based and imagery-based encoding will be given (e.g., "The wax from the candle poured onto the table", or an image of a candle scorching a table) and will be developed as the treatment is manualized. Immediately following list presentation, the cue word will be presented without the target (e.g., "candle-_____") and the participant will be asked to generate the target. Spontaneous production of targets will be recorded. For each item not spontaneously recalled, participants will be asked to retrieve the

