6.2.3.1. Procedure. Six biweekly sessions of EL will be conducted, each using two VPA lists and two FNP lists. During EL, the word pairs (e.g., "candle-table") or face-name pairs will be presented in horizontal arrangement on a computer screen at a rate of 1 per 6 seconds with no encoding instructions. After initial presentation, the cue will be presented without the target. For VPA learning, the cue word in each pair ("candle - _____") will be presented, and the participant will be asked to provide the second (target) word, ***but only if they are certain they can retrieve it accurately. Guessing is explicitly discouraged.*** If the participant cannot provide the word within 3 seconds, the word appears on the screen for 3 seconds and the participant is asked to read the pair aloud. During training, each list will be presented five times in this fashion. The dependent measure is the percent correct target words produced (out of 12) during the fifth exposure trial for each list. The procedure will be repeated for the second VPA list and then for the two FNP lists, yielding 4 accuracy measures (percent correct) for each session.

6.2.4. Retrieval Practice (RP). Some authors have argued that practicing retrieval during learning is an essential feature of successful learning^{10,47}. Effects of RP are most robust when retrieval is effortful, successful and spaced over time^{48,49}. If retrieval of a learned item is practiced shortly after it is learned, but before it is forgotten, subsequent recall is enhanced, a phenomenon known as the "testing effect"⁴⁷. RP has been used recently to improve performance of memory-impaired patients with multiple sclerosis⁵⁰ and M-STBI^{11,19}.

6.2.4.1. Procedure. Six biweekly sessions of RP will be conducted. We will follow procedures outlined in Sumkowski et al¹⁹, who demonstrated efficacy of RP in a small group of patients with M-STBI and chronic memory deficits. For each session, two sets of 12 VPA's and 12 FNP's will be used. Paired stimuli will be presented together for 6s on a computer screen, and the participant will be asked to read the VPA or say the name (FNP) aloud. Following this, 3 6s filler pairs (other VPA's or FNP's) will be presented. Then, a 5s cued

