recall test (candle-_____), followed by a 1-s feedback screen (candle-table) will be presented, followed by another six 6s filler trials and another 5s cued recall test and 1s feedback. This continues until all 12 VPA's or FNP's are given. After VPA is complete, FNP is administered (counterbalanced). After a brief delay, the participant completes two separate delayed cued recall tests (VPA, FNP, counterbalanced). The procedure is repeated for the second set of VPA's and FNP's. Dependent measure: Percent correct scores on the delayed recall test for each of the two VPA and two FNP sets, recorded each session.

6.2.5 Manualization and Fidelity Testing. During Phase 1, session-by-session procedures, including instructions to therapists and patients, stimuli and stimulus presentation schedules, methods of data collection, and permissible procedural variations will be formalized into a treatment manual for each of the three interventions. Six Master's level therapists will be trained in all three interventions, and will practice administering them to volunteer participants. At the end of Phase 1, each therapist will administer each treatment to a Veteran participant with M-STBI. Each session will be video recorded for evaluation of treatment fidelity by the study team^{51,52}, which will review session recordings and will rate the degree to which the therapist adhered to the following aspects of the protocol: communication of content to the participant (consent, rationale for treatment, instructions for engaging in training), accurate use of cues, selection of stimulus materials, recording of data, and adherence to designated treatment schedules. We will develop a rating sheet that provides feedback to therapists on their adherence to the manualized protocol⁵³.

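### The stated pool of 144 word pairs and 144 face-name pairs covers one treatment, so read literally each participant's second treatment re-presents pairs trained in the first

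*Protocol*

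**What the plan says.** Protocol 6.2.1, on materials common to the interventions, states: "Each of the three treatment conditions will utilize the same training materials". It specifies two 12-item verbal paired-associate (VPA) lists and two 12-item face-name pair (FNP) sets per session, "for an overall total of 144 unique VPAs and 144 FNPs".

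The treatment sections repeat the per-session load:

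- Memory strategy training (MST, 6.2.2.1): "Two VPA lists and two FNP lists will be used in each session".
- Errorless learning (EL, 6.2.3.1): "Six biweekly sessions of EL will be conducted, each using two VPA lists and two FNP lists".
- Retrieval practice (RP, 6.2.4.1): "For each session, two sets of 12 VPA's and 12 FNP's will be used".

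Section 6.4.2 gives each participant two treatments, one matched and one mismatched, each of six sessions over three weeks. "One participant will be assigned to each treatment order in Table 4", which makes four people per deficit group and 12 in all. On interference between treatments it says that "carryover effects are typically small and counterbalancing the order of treatments should further reduce treatment carryover".

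Section 6.2.5 leaves detail to Phase 1: "stimuli and stimulus presentation schedules, methods of data collection, and permissible procedural variations will be formalized into a treatment manual".

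SAP 2.6 takes session-by-session percent correct on VPA and FNP probes, with post-treatment and 1-month probes, as Phase 3 memory data. It compares matched with unmatched treatment within each individual.

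**The concern.** If the pool holds 144 pairs of each type and one treatment uses all of them, the second treatment has only used pairs to draw on. By then each pair has had five training trials (MST or EL), or a study trial, two cued tests with feedback and a delayed test (RP). Second-block scores would mix the effect of the second treatment with what remains from the first.

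The direction is not obvious. Earlier learning could raise second-block scores. The protocol's own account of EL (6.2.3) holds that errors made in training persist and harm relearning, so errors made under MST or RP could lower later EL scores on the same pairs. A participant coming from MST would also bring a sentence or image for each word pair into EL, which is meant to give no encoding instructions. Repeated items could thus blur the contrast between treatments that Hypothesis A tests.

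A 1-month probe of pairs trained under both treatments could not be credited to either one. Protocol section 5 says the results will help to power a larger trial, so distorted individual effect sizes could carry forward.

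**Working it through.** **Inputs.** Two lists of each type per session and 12 items per list (6.2.1); six sessions per treatment and two treatments per participant (6.4.2); treatment orders from Table 4.

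**1. Reproduce the stated total.** Lists x items x sessions:

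- One treatment: 2 x 12 x 6 = 144. This matches the protocol exactly.
- Two treatments, as one participant receives: 2 x 12 x 12 = 288.
- Three treatments with separate sets: 2 x 12 x 18 = 432.

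**2. Overlap.** If pairs are unique within a treatment, which is how 144 arises, the overlap between a participant's two treatments is 144 + 144 - 144 = 144, or 100%. Under any other allocation, 144 pairs still cannot fill 288 slots without repeats. For example, 72 pairs per treatment would keep the treatments apart but repeat pairs within each.

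**3. Interval.** With evenly spaced twice-weekly sessions and no break between treatments (assumptions), a list kept in the same session position returns after 6 x 3.5 = 21 days. If lists are reshuffled, the range is 1 x 3.5 = 3.5 days to 11 x 3.5 = 38.5 days.

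**4. What counterbalancing removes.** Let s_ij be an additive re-exposure effect on the second block in order ij (1 = MST, 2 = EL, 3 = RP). It enters the matched-minus-mismatched difference as -s_ij if matched is first and +s_ij if matched is second.

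- Matched first: encoding 12, 13; consolidation 21, 23; retrieval 31, 32 (six people).
- Matched second: encoding 21, 31; consolidation 12, 32; retrieval 13, 23 (six people).

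Each of the six orders appears once in each row, so the 12-person sum is exactly 0. The encoding-group sum is -s12 - s13 + s21 + s31, which is zero only if those effects happen to balance; the other groups are analogous. Each individual's difference keeps its full s_ij.

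**5. Scale, by assumption only.** The documents give no size for s. One pair in a 12-pair list is 1/12 = 8.3 percentage points. With no ceiling and the same effect in every order:

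| Extra pairs recalled per list | Shift in one person's difference | Gap between orders (2 x shift) |
|---|---|---|
| 0 | 0 | 0 |
| 1 | 8.3 | 16.7 |
| 2 | 16.7 | 33.3 |
| 3 | 25.0 | 50.0 |

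The shift is upward if matched is second and downward if matched is first; interference would reverse the signs. A shift equal across all six sessions moves level and non-overlap measures but not improvement rate.

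**The case against.** The strongest reply is that 144 is a per-treatment count. The sentence starts from what one session contains and multiplies out to six sessions, and common materials may mean the same kind of material. The manuals are to fix stimulus schedules, and 6.2.5 makes selection of stimulus materials a rated fidelity item, which suggests that some selection rule was intended. The SAP also points to a Section 2.2 that is not in the text available here. This stands as a real possibility. Against it, the protocol calls the total an overall one and places it in the section on shared materials, and the supplied text mentions neither alternate forms nor allocation of lists to treatments.

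Second, section 6.4.2 acknowledges multiple-treatment interference, counterbalances for it and allows a comparison of treatments given first with those given second. That also stands: additive order effects cancel in the 12-person mean, and a first-versus-second comparison could show re-exposure, though mixed with other order effects. It does not repair the individual comparisons that the SAP plans.

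Third, VPA and FNP scores are not the only outcome. Aim 2 names memory component performance as primary, 6.4.2 calls VPA and FNP performance proximal, and section 6.5 adds memory tests and everyday-memory simulations that are not said to use trained pairs. This limits the reach of the point.

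Fourth, reusing one set holds item difficulty constant, while separate pools bring in a difficulty difference that balances only on average. That is a genuine trade-off. MST and EL are also scored on the last training trial, where a ceiling could shrink any gain.

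**Conclusion.** The point holds as a conflict between a stated number and the design. A pool of 144 pairs of each type fills one treatment; each participant has two and needs 288. On the literal reading, all 144 second-treatment pairs of each type are repeats, for all 12 participants. Level and non-overlap measures in each individual's matched-versus-mismatched comparison would then be biased by an amount and in a direction the documents do not give.

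A reader might infer more, and the documents do not support it:

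- That re-presentation of every pair is settled fact. A per-treatment count remains possible, and the manuals are not supplied.
- That the overall matched-versus-mismatched result is biased. An additive effect that depends only on order contributes zero to the 12-person mean.
- That every Phase 3 outcome is affected. The point concerns the trained-pair scores, and the 1-month probe only if it uses trained pairs.
- That the 8.3 to 25.0 point shifts are estimates. They are an assumed range that includes zero and ignores ceilings.

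General order and carryover effects would remain even with separate lists. The point is only the added re-exposure to items. It should be fixed; confidence is medium because of the open wording.

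**What to change.** In 6.2.1 and the manuals, state that a participant's two treatments use disjoint lists. Build two equated pools, A and B, each of 144 VPAs and 144 FNPs (288 of each in total), meeting the stimulus criteria already in 6.2.1. RP filler pairs are extra if they are not drawn from the pools.

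Counterbalance the pools over Table 4. One schedule that works:

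- Pool A first: encoding 12 and 21; consolidation 23 and 32; retrieval 31 and 13.
- Pool B first: encoding 13 and 31; consolidation 21 and 12; retrieval 32 and 23.

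Each of the six orders then has one A-first and one B-first participant, as does each deficit group's matched-first pair and matched-second pair. Each treatment uses each pool four times, and the matched treatment uses each pool six times.

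State which pairs are probed at 1 month, and score any trained pair by the treatment in which it was trained.

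If 144 was meant per treatment, correct the wording to the true pool size (288 of each for two pools, 432 for separate sets in all three treatments) and state how lists are allocated.

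The cost is Phase 1 work to source and equate 144 more pairs of each type; whether the named photograph source can supply the faces is not stated. Residual differences in pool difficulty would be confounded with treatment within a person and balance only on average. No sessions, visits or participants are added. If separate lists already exist, the cost is a corrected sentence and a stated allocation rule.
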